3.4.1.2 Objective Response Rate (ORR)

Objective response rate according to RECIST v1.1 (or iRECIST for Part B only) is defined as the percentage of patients with a best overall response of CR or PR (or iCR or iPR) out of all patients in the efficacy analysis set for the given group (dose level, cohort, or arm).

Overall ORR and ORR by 6 weeks, by 9 weeks, by 12 weeks, and by 15 weeks post start of study treatment will be derived. As the Week 6 and Week 12 tumor response assessments have protocol-specified windows of day 39-43 and day 79-85 respectively, assessments on day 43 (6 weeks + 1 day) and day 85 (12 weeks + 1 day) will be counted toward ORR for their respective weeks. ORR will be derived for the following combinations of conditions:

- Based on investigator RECIST v1.1 assessment, requiring CR/PR confirmation,
- Based on investigator RECIST v1.1 assessment, without CR/PR confirmation,
- Based on central RECIST v1.1 assessment, requiring CR/PR confirmation (part B only),
- Based on central RECIST v1.1 assessment, without CR/PR confirmation (part B only),
- Based on investigator iRECIST assessment, requiring iCR/iPR confirmation (part B only),
- Based on investigator iRECIST assessment, without iCR/iPR confirmation (part B only),

- Based on central iRECIST assessment, requiring iCR/iPR confirmation (part B only),
- Based on central iRECIST assessment, without iCR/iPR confirmation (part B only).

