7.1.6 Schedule of Assessments

Table 7-1 Schedule of Assessments (2-week Dosing Interval; APPLIES TO ALL PARTS [A, A-2 AND B] OF THE STUDY)

Period	Screening Period*		Treatment Period ^d (2-week Dosing Interval/4-Week Treatment Cycles)				Follow-up Period ^a	Survival Follow-up ^b
Visit Name	Pre-Screen (Cohorts B2, B3, B5 and B8 only) ^{bb,dd,ee}	Screening	Cycle Day 1 Treatment Visit ^e	Cycle Day 15 Treatment Visit ^e	Cycle 1 Day 21±3 ^{gg} (Biopsy Visit)	Imaging and Treatment Response Assessment Visits ^c	Follow-up (FU) 1, FU2, and FU3 Visits	
Time point (Day / Week)	Day -42 to -29	Day -28 to -1	C1: Day 1 / Week 1 C2: Day 29±2 / Week 5 C3: Day 57±3 / Week 9 C4: Day 85±3 / Week 13 C5: Day 113±3 / Week 17 C6: Day 141±3 / Week 21 C7: Day 169±3 / Week 25 C8: Day 197±3 / Week 29	C1: Day 15±2 / Week 3 C2: Day 43±2 / Week 7 C3: Day 71±3 / Week 11 C4: Day 99±3 / Week 15 C5: Day 127±3 / Week 19 C6: Day 155±3 / Week 23 C7: Day 183±3 / Week 27 C8: Day 211±3 / Week 31 ^e		Day 39-43 / Week 6 (Pt A-2 and B only) Day 52-56 / Week 8 (Pt A only) Day 79-85 / Week 12 (Pt A-2 and B only) Day 108-112 / Week 16 (Pt A only) Day 120-127 / Week 18 (Pt A-2 and B only) Day 164-168 / Week 24 (Pts A, A-2 and B) Day 220-224 / Week 32 (Pts A, A-2 and B) ^c	FU1: 0 to 30 days post discontinuation FU2: 60 days ± 7 post discontinuation FU3: 90 days ± 7 post discontinuation	Every 3 months ± 7 days
ICF/HIPAA ^f	x ^{bb}	x						
Eligibility Criteria		x						
Demographics & medical history ^{g,h}		x						
Diagnosis & confirmation stage		x						
Tumor-specific therapy history ^{ff}		x						
Hepatitis B and C, & HIV testing ⁱ		x						
CD4 T-cell count ^l		x						
Covid-19 vaccination confirmation or negative Covid-19 polymerase chain reaction (PCR) test		x						
NM21-1480 infusion ^g			x	x				
Vital signs ^k		x	x	x			x	
Height		x						
Weight		x	x (Odd-numbered cycles only)				x (FU1 only)	
Physical exam ^l		x	x	x			x	
Oxygen saturation ^m			x	x				
ECOG performance		x	x	x			x	

Period	Screening Period*		Treatment Period ^d (2-week Dosing Interval/4-Week Treatment Cycles)				Follow-up Period ^a	Survival Follow-up ^b
Visit Name	Pre-Screen (Cohorts B2, B3, B5 and B8 only) ^{bb,dd,ee}	Screening	Cycle Day 1 Treatment Visit ^c	Cycle Day 15 Treatment Visit ^c	Cycle 1 Day 21±3 ^{gg} (Biopsy Visit)	Imaging and Treatment Response Assessment Visits ^c	Follow-up (FU) 1, FU2, and FU3 Visits	

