3 STATISTICAL METHODOLOGY

3.1 General Considerations

3.1.1 *Analysis Groupings*

Unless specified otherwise, analyses for Part A will be presented by dose level and in total, analysis for Part A-2 will be presented in total, and analysis for Part B will be presented by cohort and in total. Additionally, for the analysis of demographic, safety, PK, and immunogenicity data, a total for all patients across Part A and Part A-2 will be presented, as will a total for all Part B patients who received NM21-1480, and a total for all patients in any part who received NM21-1480 at the 800 mg dose level.

3.1.2 *Analysis Day*

Analysis day will be calculated from the date of first dose of study treatment. The day of the first dose of study drug will be Day 1, and the day immediately before Day 1 will be Day -1. There will be no Day 0.

3.1.3 *Definition of Baseline*

Baseline is defined as the last measurement prior to the start of study treatment.

3.1.4 *Summary Statistics*

Categorical data will generally be summarized with counts and percentages of subjects. The denominator used for the percentage calculation will be clearly defined. Continuous data will generally be summarized with descriptive statistics including n (number of non-missing values), mean, median, standard deviation, minimum, and maximum.

3.1.5 *Hypothesis Testing*

No hypothesis testing will be provided.

3.1.6 *Evaluation of Site Effect*

Site effect will not be analyzed.

3.1.7 *Handling of Missing Data*

Unrecorded data values will be recorded as missing. Only recorded (i.e. complete) data values will be used for statistical analyses. In general, invalid or missing values will not be imputed unless stated otherwise.

- For BOR and ORR, patients in the Efficacy Analysis Set who do not have sufficient on-study tumor assessments to characterize response will be included in the denominator when calculating BOR percent and ORR, and will thus be treated as non-responders. Further details are found in section [3.4.1.1](#).
- In cases of missing or incomplete dates (e.g. AEs and concomitant medications or procedures), the missing component(s) will be assumed as the most conservative value possible. For the detailed missing/partial data handling conventions for treatment-emergent adverse events see Table 2 in Appendix A. The actual data values as they appear in the original case report forms (CRFs) will be presented in the data listings.

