3.4.1 Definition of Efficacy Endpoints

3.4.1.1 Best Overall Response (BOR)

Only tumor assessments performed before the start of any subsequent anticancer therapies and no later than 30 days after last dose will be considered in the assessment of BOR. Clinical deterioration or clinical progression noted on the end of treatment or end of study eCRFs will not be considered as documented progressive disease. BOR will be derived overall, and by 6 weeks, by 9 weeks, by 12 weeks, and by 15 weeks following the start of study treatment. As the Week 6 and Week 12 tumor response assessments have protocol-specified windows of day 39-43 and day 79-85 respectively, assessments on day 43 (6 weeks + 1 day) and day 85 (12 weeks + 1 day) will be counted toward BOR for their respective weeks. BOR will be derived for the following combinations of conditions:

- Based on investigator RECIST v1.1 assessment, requiring CR/PR confirmation,
- Based on investigator RECIST v1.1 assessment, without CR/PR confirmation,
- Based on central RECIST v1.1 assessment, requiring CR/PR confirmation (part B only),
- Based on central RECIST v1.1 assessment, without CR/PR confirmation (part B only),
- Based on investigator iRECIST assessment, requiring iCR/iPR confirmation (part B only),
- Based on investigator iRECIST assessment, without iCR/iPR confirmation (part B only),
- Based on central iRECIST assessment, requiring iCR/iPR confirmation (part B only),
- Based on central iRECIST assessment, without iCR/iPR confirmation (part B only).

Precedence for best overall response according to RECIST v1.1 is determined as follows, in descending order:

- CR – When confirmation of CR is required, at least 2 assessments of CR at least 4 weeks apart and before any progressive disease (PD). If CR is not confirmed by a subsequent CR, then for the purpose of BOR determination it will instead be considered SD if it fell ≥ 39 days after the start of treatment or NE if it fell < 39 days weeks after start of treatment. When confirmation of CR is not required, at least 1 assessment of CR before any progressive disease (PD).

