3.4.2.2 Objective Response Rate (ORR)

The objective response rate for each given group (dose level, cohort, or arm) in the Efficacy Analysis Set will be summarized according to RECIST v1.1 (and according to iRECIST), accompanied by a 2-sided exact 95% Clopper-Pearson confidence interval. ORR will be presented separately for each combination of conditions described in section [3.4.1.2](#). The summaries of ORR using confirmed vs unconfirmed CR/PR (or iCR/iPR) and for overall, by 6 weeks, by 9 weeks, by 12 weeks, and by 15 weeks after the start of study treatment will all be presented in a single table.

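### If confirmation must fall inside the landmark, the scheduled scans leave the confirmed response rows by 6 and 9 weeks (Parts A-2 and B) and all four confirmed rows in Part A at zero

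*SAP*

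**What the plan says.** SAP 3.4.1.1 sets the landmarks for best overall response: "BOR will be derived overall, and by 6 weeks, by 9 weeks, by 12 weeks, and by 15 weeks following the start of study treatment". SAP 3.4.1.2 sets the same four for ORR: "Overall ORR and ORR by 6 weeks, by 9 weeks, by 12 weeks, and by 15 weeks post start of study treatment will be derived". Neither section makes an exception for Part A. Both list versions with and without confirmation: investigator RECIST 1.1 for all parts and, for Part B only, central RECIST 1.1 and investigator and central iRECIST.

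On confirmation, SAP 3.4.1.1 reads: "When confirmation of CR is required, at least 2 assessments of CR at least 4 weeks apart". PR, iCR and iPR carry the same 4-week interval. In the confirmed version, an unconfirmed CR or PR becomes SD if it fell at least 39 days after the start of treatment, and otherwise NE.

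On which scans belong to a landmark, SAP 3.4.1.2 says that "assessments on day 43 (6 weeks + 1 day) and day 85 (12 weeks + 1 day) will be counted toward ORR" for their respective weeks. No extra day is given for Weeks 9 and 15. SAP 3.1.2 fixes the day count: "The day of the first dose of study drug will be Day 1".

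On presentation, SAP 3.4.2.2 begins: "The summaries of ORR using confirmed vs unconfirmed CR/PR (or iCR/iPR) and for overall, by 6 weeks, by 9 weeks". All of these summaries go into one table, and ORR carries an exact Clopper-Pearson interval.

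The scan schedule is in Protocol 7.1.6, Table 7-1. For Parts A-2 and B the first entry is "Day 39-43 / Week 6 (Pt A-2 and B only"; the next are Day 79-85 and Day 120-127. Part A scans at Day 52-56 and Day 108-112. Protocol 10.6.2 planned response tabulations at 6 and 12 weeks for Part B and at 8 and 16 weeks for Parts A and A-2. The protocol synopsis puts Part A-2 with Part B at 6 and 12 weeks.

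**The concern.** The two early landmarks leave no room for a confirming scan. A patient whose tumour responds at the first scan and is still responding at the second would appear as stable disease in the confirmed 6- and 9-week rows, next to an unconfirmed row that shows the response. A zero with an exact confidence interval reads as though confirmation was sought and not obtained, when the scan calendar did not allow it.

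The stake is how the response tables are read. BOR is the Part B primary efficacy endpoint for the three cohorts that enrolled (SAP 2.8.1 and Section 6: 5 patients in B1, 5 in B7, 10 in B8). At these sizes, moving one patient from PR to SD shifts a row by 20 percentage points (1/5) or 10 (1/10).

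**Working it through.** **Inputs.** Landmarks, the 28-day confirmation interval and the day count come from SAP 3.1.2, 3.4.1.1 and 3.4.1.2. Scan windows come from Protocol Table 7-1. Cohort sizes come from SAP Section 6.

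**The plan's own cut-offs.** 6 × 7 + 1 = 43 and 12 × 7 + 1 = 85, as stated in the SAP. For 9 and 15 weeks I tried both conventions: 63 or 64, and 105 or 106.

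**Condition.** If both scans must fall by the landmark, a confirmed response needs first-response day + 28 ≤ cut-off, so the first response must come by cut-off − 28.

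| Landmark | Cut-off day | Latest first response | A-2/B scheduled scans that can be confirmed | Part A scheduled scans that can be confirmed |
|---|---|---|---|---|
| 6 weeks | 43 | 15 | none | none |
| 9 weeks | 63/64 | 35/36 | none | none |
| 12 weeks | 85 | 57 | Week 6, by the Week 12 scan | none: next scan Day 108 |
| 15 weeks | 105/106 | 77/78 | Week 6, by the Week 12 scan | none: next scan Day 108 |

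**Parts A-2 and B.**
- The earliest confirmation is Day 39 + 28 = Day 67, after Day 43 and after Day 63/64. An extra scan after the Week 6 visit does not help.
- By 12 weeks, the pair Week 6 and Week 12 works: the minimum gap is 79 − 43 = 36 days.
- A response first seen at Week 12 cannot be confirmed before 79 + 28 = Day 107, and on schedule not before Day 120. Both are after Day 105/106. On schedule, the 15-week confirmed row therefore holds the same responders as the 12-week row.

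**Part A.**
- The second scheduled scan, Day 108 at the earliest, is after every landmark, so all four confirmed rows are zero on schedule.
- The first scan, Day 52 at the earliest, is after Day 43, so the unconfirmed 6-week row is zero too.
- An unscheduled confirming scan from 52 + 28 = Day 80 could fill the 12- and 15-week rows.

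**How many rows.** In Part B, 4 confirmed versions × 2 landmarks = 8 of 4 × 4 = 16 confirmed landmark ORRs per cohort are zero on schedule. Part A-2 has one confirmed version, with 2 of 4 rows zero. In Part A it is 4 of 4.

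**What would be printed.** The Clopper-Pearson upper limit for 0/n is 1 − 0.025^(1/n): 0.522 for n = 5 and 0.308 for n = 10, if every enrolled patient is in the Efficacy Analysis Set.

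**Illustrative patients.**
- Part B, PR on Day 42 and Day 84: confirmed BOR is SD by 6 and 9 weeks, PR by 12 and 15 weeks.
- Part B, SD on Day 42, PR on Day 84 and Day 124: SD at all four landmarks, PR overall.
- Part A, PR on Day 54 and Day 110: NE by 6 weeks, SD by 9, 12 and 15 weeks, PR overall.

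**If the landmark dated the first response instead.** In A-2/B, Week 6 responders confirmed later would count from the 6-week row on and Week 12 responders from the 12-week row on. No A-2/B row would be forced to zero.

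**The case against.** The strongest objection is that the SAP never says the confirming scan must fall by the landmark. It says which assessments count toward Weeks 6 and 12, and it describes an unconfirmed PR as one with no subsequent PR or CR, without a time limit. If the landmark dates only the first response, no A-2/B row is forced to zero. This stands as an ambiguity. But the text works by assigning assessments to landmarks. If Day 43 needs a special allowance to count toward Week 6, a Day 84 scan does not count toward it, and a programmer would reasonably build it that way.

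A reader might infer that no patient could ever have a confirmed response by 6 or 9 weeks. The documents do not support that. The SAP has rules for responses seen before 39 days, so it foresees off-schedule scans. A first response by Day 35/36 and a second by Day 63/64 would count by 9 weeks. No scan is scheduled that early, so the zeros are zeros on schedule.

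A reader might also infer that the whole confirmed BOR row is empty. Only its CR and PR categories are. Those patients move to SD, or possibly to NE for a scan on Day 39, which is 38 elapsed days after Day 1.

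Leaving a response first seen at Week 12 out of the 15-week confirmed row is not an error in itself. It is a legitimate meaning of confirmed by 15 weeks, though one the SAP should state.

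Finally, the impact is limited. The protocol already planned 6- and 12-week tabulations for Part B and confirmed and unconfirmed sets (10.6.2, 10.6.2.2, 10.6.2.3). The table shows both versions, and responses are listed by patient. The SAP plans no hypothesis test (3.1.5) and no interim analysis (5.1). All of this stands, and it limits the weight of the point.

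**Conclusion.** The point holds for descriptive landmark rows, and only on two assumptions: that assessments after the landmark do not count toward it, and that scans follow Table 7-1. On that basis confirmed CR/PR is zero by 6 and 9 weeks in Parts A-2 and B, the 15-week confirmed row adds nothing to the 12-week row, and Part A has four empty confirmed rows and one empty unconfirmed row.

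Part A is the worse case, and the mismatch arose in the SAP. The protocol's 16-week landmark (Day 112) would have captured a Day 52-56 response confirmed at Day 108-112. SAP Section 6, on changes from the protocol, does not mention the new landmarks.

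A reader might infer that the Part B primary endpoint is compromised. It is not: SAP 2.8.1 names BOR without a landmark, and overall confirmed BOR and ORR are unaffected, as are the unconfirmed A-2/B rows. The harm is a set of zeros, with intervals attached, that say nothing about the drug. It is worth correcting because it is easy to misread and cheap to avoid.

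**What to change.** In SAP 3.4.1.1 and 3.4.1.2, state that a confirmed response counts by Week X if its first CR/PR is dated by Week X and it is confirmed at any later assessment at least 4 weeks after, within the SAP's existing limits on progression, subsequent therapy and 30 days after last dose.

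If the sponsor prefers confirmation inside the landmark, say so and drop the confirmed rows that cannot be non-zero on schedule: 6 and 9 weeks in Parts A-2 and B, all four in Part A.

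In either case, replace 6, 9, 12 and 15 weeks in Part A with the protocol's 8 and 16 weeks. The first-response rule alone would not fill Part A's 6-week row. With confirmation inside the landmark, the confirmed 8-week row would also have to go, because 52 + 28 = Day 80 is after Day 56/57. Record the change of landmarks in SAP Section 6.

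The cost is one SAP sentence, a changed date variable in the program and a different set of Part A rows. No new data are needed.

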3.4.1.3 Progression-Free Survival (PFS)

Progression-free survival will be defined as the time from the start of study treatment until the earliest documented date of disease progression (PD) or death for all patients in the Efficacy Analysis Set. Clinical deterioration or clinical progression noted on the end of treatment or end of study eCRFs will not be considered as documented progressive disease.

The event and censoring rules for PFS are summarized as follows:

Table 1 Date of Event or Censoring for PFS

Situation	Date of event or censoring	Outcome
Death	Date of death	Event
Progressive disease	Date of PD Assessment	Event
Initiation of subsequent anticancer treatment prior to relapse or death	Date of last evaluable disease assessment prior to start of subsequent anticancer treatment	Censored
Missing (or NE at) two or more consecutively scheduled disease assessments directly preceding a PD	Date of last evaluable disease assessment before the first missed (or NE) visit	Censored
Withdrawal from Study	Date of last evaluable disease assessment before study withdrawal	Censored
Alive without relapse and without initiation of subsequent anticancer treatment	Date of last evaluable disease assessment	Censored

If a patient has no evaluable (non-NE) post-baseline disease assessments or starts a subsequent anti-cancer therapy before having any evaluable post-baseline disease assessments, then they will be censored at start of study treatment. SD assessments, unconfirmed PR assessments, and unconfirmed CR assessments that falls within <39 days after the start of study treatment are considered evaluable post-baseline assessments for the purpose of PFS derivation (though they are counted as NE for BOR and ORR derivation).

PFS will be derived for the following combinations of conditions:

- Based on investigator RECIST v1.1 assessment,
- Based on central RECIST v1.1 assessment (part B only).

3.4.1.4 Overall Survival (OS)

Overall survival will be defined as the time from the start of study treatment until death due to any cause. Patients alive at the data cut-off date will be censored for survival at their last contact date. The date of last contact date will be the latest complete date among but not limited to the following:

- Date last known to be alive collected on the eCRF form “Survival Status” (only to be used if status is “Alive”),

- All patient assessment dates (e.g., laboratory blood draws, vital signs, performance status, ECGs, physical examination, tumor response assessment, and other study procedure dates),
- Start and end dates of concomitant medication and/or subsequent anti-cancer therapies,
- Study treatment start and end dates,
- AE start and end dates,
- Other available clinical data which can confirm patient's survival status,
- Date of discontinuation from End of Study eCRF forms (not to be used if reason for discontinuation is lost to follow-up).

3.4.2 Analysis of Efficacy Endpoints

3.4.2.1 Best Overall Response (BOR)

The number and percent of patients with each best overall response for each given group (dose level, cohort, or arm) in the Efficacy Analysis Set will be summarized separately for RECIST v1.1 and iRECIST for each combination of conditions described in section [3.4.1.1](#). The summaries of BOR using confirmed vs unconfirmed CR/PR (or iCR/iPR) and for overall, by 6 weeks, by 9 weeks, by 12 weeks, and by 15 weeks after the start of study treatment will all be presented in a single table.

For patients with BOR of Not Evaluable, the reason for non-evaluability will be summarized:

- No baseline assessment
- No adequate post-baseline assessment
- All post-baseline assessments have overall response of "NE"
- New anticancer therapy started before first post-baseline assessment
- Only post-baseline assessment was stable disease <39 days after the start of study treatment
- First evaluable post-baseline assessment was progressive disease >12 weeks after start of study treatment.

The investigator assessed RECIST v1.1 responses will be summarized for each of the planned response assessment timepoints with percentage based on the number of patients with available response assessments for the respective timepoint. For Part B, the iRECIST response assessments by timepoint will be likewise summarized.

All tumor measurements, sums of diameters, investigator and central response assessments according to RECIST v1.1 and iRECIST, and all derived BORs (overall, by 6 weeks, by 9 weeks, by 12 weeks, and by 15 weeks post start of study treatment) will be listed by patient.

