10.6.2 Efficacy Analyses

In order to perform preliminary evaluation of anti-tumor activity, BOR outcomes, ORR, and disease control rate (DCR) according to RECIST 1.1 and iRECIST will be tabulated by frequency distribution overall, and 6 and 12 weeks following the start of study treatment for Part B cohorts as determined by central and institutional reads. Similar exploratory analyses as determined by institutional reads (but for RECIST1.1 only) will be done for Part A and A-2 (if applicable) overall, and 8 and 16 weeks following Day 1, in accordance with the respective imaging visit frequency.

Median TTR and duration of response (DOR) will be summarized for those patients with responses, using the Kaplan-Meier method, i.e., by generation of Kaplan-Meier curves for time-to-event variables; PFS and OS will be similarly summarized. Individual tumor measurements, tumor burden and % changes in tumor burden will be listed. Changes in tumor burden will be presented graphically for each tumor-type. All primary clinical activity analyses will be based on the Efficacy Analysis Set, ongoing patients who have not reached the first post-baseline tumor assessment will be excluded from response analyses. Exploratory analysis to assess the OS will be provided by a Kaplan-Meier method. Summary statistics and plots of measures of tumor-specific antigen levels may be provided if applicable.

Efficacy data will be presented in tabular and/or graphical format and summarized descriptively by dose level in Part A, Part A-2 and Part A/A-2 combined, and by cohort in Part B. Dose groups in Part B may be pooled within cohorts for final analyses if the response is deemed to be independent of dose from a clinical perspective.

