6 CHANGES FROM PROTOCOL-SPECIFIED STATISTICAL ANALYSIS

Only limited patients were enrolled onto the study under Cohort B1 (5 patients), Cohort B7 (5 patients) and Cohort B8 (10 patients) in Part B. Cohort A-2 only enrolled 5 patients. There are no patients enrolled under Cohort B2, Cohort B3, Cohort B4, Cohort B5 and Cohort B6 in Part B. Therefore, due to the limited data, only related TFLs will be generated and no interim analyses were performed.

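### The SAP's by-timepoint response table counts only patients scanned at that visit, and the protocol's displays of change in tumour burden are missing from the SAP without being declared

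*SAP*

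**What the plan says.** SAP 3.4.2.1 plans a table of investigator-assessed RECIST 1.1 response at each scheduled assessment, "with percentage based on the number of patients with available response assessments for the respective timepoint". The same is done for iRECIST in Part B. No row is specified for patients without an assessment.

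BOR and ORR follow a different rule. SAP 3.1.7 states that Efficacy Analysis Set patients with too few tumour assessments "will be included in the denominator when calculating BOR percent and ORR, and will thus be treated as non-responders". On that basis SAP 3.4.1.2 says: "Overall ORR and ORR by 6 weeks, by 9 weeks, by 12 weeks, and by 15 weeks post start of study treatment will be derived". BOR has the same cuts (SAP 3.4.1.1), and ORR is "accompanied by a 2-sided exact 95% Clopper-Pearson confidence interval" (SAP 3.4.2.2). BOR is the primary efficacy endpoint for the Part B cohorts that enrolled (SAP 2.8.1). Those are "Cohort B1 (5 patients), Cohort B7 (5 patients) and Cohort B8 (10 patients) in Part B" (SAP section 6).

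On tumour burden, protocol 10.6.2 commits to a listing of individual measurements, burden and percentage change, and adds: "Changes in tumor burden will be presented graphically for each tumor-type". SAP 3.4.2.1 lists measurements and sums of diameters by patient. Nowhere in SAP 3.4 is there a percentage change or a plot of tumour burden. SAP section 6 says in general terms that only relevant outputs will be produced because data are limited; it does not mention this omission.

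**The concern.** Whether a patient has a scan at a late visit depends on how that patient has done. Under protocol Table 7-1, footnote e, imaging runs until discontinuation criteria are met. Footnote v limits follow-up imaging to a single scan in patients who stopped without documented progression. Patients who progressed or died early therefore tend to leave the denominator while responders stay in it. A reader following the by-timepoint table across visits could take attrition for a rising response rate.

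In cohorts this small, few or no responders may be seen, and the size of tumour shrinkage then carries much of the activity information. The protocol uses it in this way. Its rationale for the colorectal cohort (section 5.2) cites an unconfirmed partial response at Week 16, with liver metastases reduced in diameter by roughly half or more. In the version of BOR that requires confirmation, the SAP classes such a response as stable disease, so the shrinkage is not visible in that table.

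**Working it through.** **Plan's own figure.** The disputed sentence states no number. The only design figure for response in the single-arm cohorts is the BOP2 power of 0.9152 at a 20% response rate (protocol 10.3.3). The exact two-stage binomial, P(at least 2 responders in 25 and at least 5 in 40), gives 0.9152, so it reproduces. Nothing below depends on it.

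**Which scans have a full-denominator summary.** Set the Table 7-1 scan schedule beside the SAP's by-week cuts:

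| Part | Scheduled scans within the 6, 9, 12 and 15-week cuts | Scheduled scans after 15 weeks (Day 105) |
|---|---|---|
| A | Week 8 (Day 52-56) | Week 16 (Day 108-112), 24, 32 |
| A-2 and B | Week 6 (Day 39-43), Week 12 (Day 79-85) | Week 18 (Day 120-127), 24, 32 |

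For the right-hand column, overall BOR and ORR still count the response, but the only time-specific summary is the table with the available-assessment denominator. Protocol 10.6.2 asked for a 16-week result in Part A; the 15-week cut closes before that scan window opens.

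**One responder, two denominators.** Let r be responders, m patients scanned at the visit and N patients in the Efficacy Analysis Set. The SAP table shows r/m; the full-set figure is r/N. The values of m are assumed, and N is taken as everyone enrolled.

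| Cohort | r/N | r/m as m falls |
|---|---|---|
| B1 or B7, N = 5 | 1/5 = 20.0% | 1/4 = 25.0%, 1/3 = 33.3%, 1/2 = 50.0% |
| B8, N = 10 | 1/10 = 10.0% | 1/8 = 12.5%, 1/6 = 16.7%, 1/4 = 25.0% |

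**Average effect.** Suppose all responders are scanned and a share q of non-responders is scanned. With true rate p, the expected displayed rate is p / (p + (1 - p)q).

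- p = 0.10: q = 0.8 gives 0.10/0.82 = 12.2%; q = 0.6 gives 0.10/0.64 = 15.6%; q = 0.4 gives 0.10/0.46 = 21.7%.
- p = 0.20: q = 0.8 gives 0.20/0.84 = 23.8%; q = 0.6 gives 0.20/0.68 = 29.4%; q = 0.4 gives 0.20/0.52 = 38.5%.

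Simulation at N = 5 and N = 10 agrees to within about 0.1 percentage points. The q values are assumptions; the documents give no retention figures.

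**The direction can reverse.** If the only responder of 5 misses a visit that the other 4 attend, the table shows 0/4 = 0% against 1/5 = 20%.

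**Coarseness is a separate matter.** One patient is 20 percentage points when N = 5 and 10 when N = 10. With no responders, the exact 95% upper limit is 52.2% (N = 5) or 30.8% (N = 10). That imprecision comes from enrolment and would remain under either denominator.

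**Tumour burden.** Of the items in protocol 10.6.2, the SAP keeps measurements and sums of diameters. It leaves out percentage change and the graph by tumour type. Percentage change follows directly from the listed sums.

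**The case against.** The best defence is that this is one supplementary descriptive table. The primary endpoint and ORR use the full set, and no hypothesis tests are planned (SAP 3.1.5). Status at a visit among those assessed is a different question from best response among all patients, and SAP 3.1.4 requires every denominator to be made clear. Some progressing patients also stay in the table. Progression counts at the visit where it is recorded, treatment beyond progression is allowed (protocol 7.1.4), and protocol 8.1.3 describes continued imaging after stopping without progression more broadly than footnote v does. On tumour burden, protocol 10.1 lets the SAP modify methods, with an amendment needed only for major changes to the primary endpoint or its analysis.

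Most of this stands, and it rules out several stronger inferences:

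- A reader might infer that the SAP's activity results in general are biased upwards. They are not: BOR and ORR, overall and by 6, 9, 12 and 15 weeks, keep unassessed patients as non-responders.
- A reader might infer that the two denominator rules contradict each other. They serve different tables.
- A reader might infer that tumour-burden data are dropped altogether, or that depth of change is the only graded measure of activity. Measurements and sums are listed, BOR is reported by category, and PFS and OS have Kaplan-Meier summaries.
- A reader might infer that the protocol requires waterfall or spider plots or best change. It names no plot type and does not mention best change.

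The defence leaves two gaps. Stating the denominator does not tell the reader why the other patients are absent, and the full-set by-week cuts end before the later scans. Freedom to modify methods does not remove the purpose of section 6, which is to record such changes. Limited data are also a weak reason for dropping a per-patient listing and plot, which suit small cohorts.

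**Conclusion.** The concern holds for a limited part of the plan. The by-timepoint response table is likely, not certain, to overstate response at later visits, and for scans after Week 15 no time-specific summary on the full Efficacy Analysis Set stands beside it. Its size cannot be fixed from the documents. If 80% down to 40% of non-responders and all responders are scanned, a true 10% rate would display on average as about 12% to 22%, and a true 20% rate as about 24% to 38%. No primary result changes.

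The second part rests on comparing the texts and needs no assumption: the percentage-change listing and the graph by tumour type promised in protocol 10.6.2 are absent from SAP 3.4 and not named in section 6. This is a gap in reporting and documentation. It biases no rate, and the underlying measurements remain available.

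**What to change.** In SAP 3.4.2.1, use all Efficacy Analysis Set patients in the dose level or cohort as the denominator at each timepoint. Add rows for progressed or died earlier, off study, and assessment not done, so that each column accounts for every patient.

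In SAP 3.4, restore the per-patient listing of percentage change in tumour burden and a plot of change by tumour type, as in protocol 10.6.2. A waterfall or spider plot would be a suitable format, but the choice is open.

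The cost is a little programming on data already collected. By-visit response rates will usually look less favourable than under the present rule.
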